 Yale Students	 Females of childbearing potential	

NOTE: Is this research proposal designed to enroll children who are wards of the state as potential subjects?

Yes No

To understand the effects of adiposity in puberty on metabolism in type 1 diabetes, we must study adolescents during puberty, and this must also occur in a pediatric population as adolescents usually complete puberty by age 18. Furthermore, this age group contains females of childbearing potential and exclusion of females would limit the findings only to males. Our group is experienced in conducting euglycemic hyperinsulinemic clamps and abdominal MRI in children. Prior published work is evidence of our scientifically rigorous process while maintaining safety for study participants.

8. **Inclusion/Exclusion Criteria:** What are the criteria used to determine subject inclusion or exclusion?

- Inclusion criteria:

All Participants:

1. Clinical diagnosis of T1D
2. HbA1c ≤9%
3. Diabetes duration of at least 12 months

Adolescents with T1D:

1. Age 12-16 years
2. BMI <75th for lean pediatric subjects, ≥ 85th percentile for overweight/obese pediatric subjects;
3. Tanner stage 2-5
4. Parent able to provide written consent and participant able to provide assent

Lean, young adults with T1D:

1. Age 18-24 years
2. BMI 18.5-24.9 kg/m²
3. Able to provide written consent.

- Exclusion criteria:

1. Use of adjunctive diabetes medications or other medications known to impact insulin sensitivity
2. Weight loss medications within the past six months
3. Current psychiatric disorders, including eating disorders (DSM-V criteria)

4. Known liver disease other than nonalcoholic hepatic steatosis
5. Females who are pregnant or lactating
6. Anemia or another medical condition that precludes participation in the study
7. Not meeting MRI safety criteria
8. Claustrophobia that will prevent participation in the MRI

9. How will eligibility be determined, and by whom? Write here
PI or co-investigators will determine eligibility after review of medical history, screening tests and inclusion/exclusion criteria through the regular clinical encounters and through review of the EMR record of patients under their clinical care

10. **Risks:** Describe the reasonably foreseeable risks, including risks to subject privacy, discomforts, or inconveniences associated with subjects participating in the research.

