- **Measures of Insulin Sensitivity:** Calculations will be conducted using methods used by Drs. [name] and [name] in previous work (41). Endogenous glucose production and fasting insulin levels will be used to calculate hepatic insulin resistance. Glycerol turnover will be utilized to assess adipose specific insulin sensitivity.

• Statistical Analysis: Descriptive statistics, such as mean, standard deviation, count, and percent, will be used to characterize the groups. Continuous variables will be compared among the three groups using the Kruskal-Wallis test or Analysis of Variance (ANOVA) for not Normal and Gaussian distributions respectively, followed by pair-wise group comparisons with either the Student's t-test or the Mann-Whitney U test, depending upon the normality in the distributional assumptions of the variables. Categorical variables will be compared with the Chi-square test or the Fisher's Exact test. Spearman Correlation will explore associations of the following assessments with measures of insulin suppression of hepatic glucose production and stimulation of peripheral glucose uptake.

- Glycemic control (HbA1c, fasting glucose)
- Additional measures of insulin sensitivity (endogenous glucose production, glycerol turnover, glucose oxidation, fat oxidation).

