Associations of these assessments with measures of insulin sensitivity will be explored for all groups. Unadjusted differences in the group means of primary and secondary outcomes of interest between lean and obese adolescent subjects, as well as between lean young adults and lean adolescent subjects, will be examined using the Student's t-test or the Mann-Whitney U test for variables with Gaussian and not normal distributions respectively. The impact of group, gender, sex hormones, pubertal stage, and growth factors on the outcome measures will also be explored using multivariable linear regression modeling. For the primary adjusted analysis, we will treat group as a categorical variable, and conduct two post-hoc pair-wise comparisons of means at alpha of 0.025. For the secondary adjusted analysis, we will also treat our three groups of subjects as an ordinal variable, whereby the lowest level will be given to the obese adolescents, followed by the lean adolescents, and then lean young adults. The latter approach will allow us to obtain a linear increase in the mean glucose disposal rate across the three groups, thus allowing us to use an alpha level of 0.05. The outcome variable will be normalized, if needed, using the natural log function.

Visit 2: Abdominal MRI: Sample Size: Based on mean hepatic lipid content in healthy overweight/obese and lean children ¹⁰, groups sizes of 36 lean and 36 obese adolescents will achieve >99% power at alpha of 0.05 to detect a difference between group means of 3.5% (SD=2) and 1.5% (SD=0.5). Even if a few subjects decline participation in this Aim, we will still have 90% power at alpha of 0.05 to detect the projected effect size using with a minimum of 12 subjects per group.

Data Analysis Approach:

The Proton Density Fat Fraction (PDFF) , a biomarker for hepatic steatosis, will be calculated from the liver images obtained liver PDFF parametric maps ⁹. A PDFF value above 5.5% is indicative of fatty liver ¹¹.

• Statistical Analysis: Descriptive statistics (mean, standard deviation, count, and percent) will be used to characterize the groups. Continuous variables will be compared between the lean and obese adolescents using either the Student's t-test or the Mann-Whitney U test. Categorical variables will be compared with the Chi-square test or the Fisher's Exact test. Associations of the following assessments with hepatic fat fraction will be explored through Spearman Correlation.

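### Liver fat is planned on SDs of 2 and 0.5, yet only Student's t or Mann-Whitney is offered; naming Welch's test is a cheap safeguard if MRI losses are uneven

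*Combined protocol and SAP*

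**What the plan says.** All of this is in Section I, item 13 (Statistical Considerations), unless noted.

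- **Planning values (Visit 2, Sample Size).** The comparison is sized "to detect a difference between group means of 3.5% (SD=2) and 1.5% (SD=0.5"). The order of the groups in that sentence makes the first pair obese/overweight and the second lean. It adds that "groups sizes of 36 lean and 36 obese adolescents will achieve >99% power at alpha of 0.05".
- **Lost scans (same paragraph).** "Even if a few subjects decline participation in this Aim, we will still have 90% power at alpha of 0.05", with a floor of 12 in each group. No loss rate is given, nor how losses would divide between groups.
- **Test (Visit 2, Statistical Analysis).** "Continuous variables will be compared between the lean and obese adolescents using either the Student's t-test or the Mann-Whitney U test". No rule for choosing between the two is given here.
- **Selection rule (Visit 1, Statistical Analysis).** There the choice is made "depending upon the normality in the distributional assumptions of the variables". Equality of variance is not mentioned.
- **Transformation (Visit 1).** "The outcome variable will be normalized, if needed, using the natural log function". Visit 2 refers back to the Aim 1 plan only for adjusted associations with the insulin sensitivity indices.

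No unequal-variance test is named anywhere in the document.

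**The concern.** Student's t pools the two variances, but the plan's own inputs put them 16-fold apart (4 against 0.25). If liver fat looked normal, the normality rule would lead straight to the pooled test.

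With equal group sizes the pooled standard error is still right on average. With unequal sizes it is not: the larger group dominates the pooled variance. If obese scans are lost, the standard error is too small and the test rejects too often. If lean scans are lost, it rejects too rarely.

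What is at stake is error control when the true difference is small or absent. That case is open here. The planning values come from healthy children, and the Background cites one MRI study in which liver fat was slightly lower in youth with type 1 diabetes than in controls (1.3% against 1.8%), with obesity not examined.

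**Working it through.** **Inputs.** Means 3.5 and 1.5, SDs 2 and 0.5, 36 or 12 per group, alpha 0.05 (all from Visit 2, Sample Size). Sidedness is not stated; two-sided is assumed.

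**1. The plan's own power.** Pooled SD = √[(2² + 0.5²)/2] = √2.125 = 1.458, and the difference is 2.

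- 36 per group: 2 / (1.458 × √(2/36)) = 5.82, giving power 99.99% (stated: above 99%).
- 12 per group: 2 / (1.458 × √(2/12)) = 3.36, giving 91.9% by the normal formula and 89.4% by noncentral t (stated: 90%).

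Both stated figures reproduce.

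**2. Why uneven numbers matter.** Compare the variance that Student's t uses with the true variance of the difference (n₁ obese, n₂ lean):

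- Used: [(n₁−1)·4 + (n₂−1)·0.25]/(n₁+n₂−2) × (1/n₁ + 1/n₂)
- True: 4/n₁ + 0.25/n₂

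| Obese:lean | Used | True | Ratio of standard errors |
|---|---|---|---|
| 36:36 | 2.125 × 0.0556 = 0.118 | 0.111 + 0.007 = 0.118 | 1.00 |
| 30:36 | 1.949 × 0.0611 = 0.119 | 0.133 + 0.007 = 0.140 | 0.92 |
| 24:36 | 1.737 × 0.0694 = 0.121 | 0.167 + 0.007 = 0.174 | 0.83 |
| 36:24 | 2.513 × 0.0694 = 0.175 | 0.111 + 0.010 = 0.122 | 1.20 |

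**3. Resulting type I error.** Simulation with equal means, normal data and nominal 5%, 1 million runs per case. The last column assumes that each group keeps its planned coefficient of variation at a common mean of 1.5: obese SD = 1.5 × 2/3.5 = 0.86, lean SD = 0.5.

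| Obese:lean | Student, SD 2/0.5 | Welch, SD 2/0.5 | Student, SD 0.86/0.5 |
|---|---|---|---|
| 36:36 | 5.3% | 5.0% | 5.1% |
| 34:36 | 5.9% | 5.0% | 5.4% |
| 33:36 | 6.3% | 5.0% | not run |
| 30:36 | 7.5% | 5.1% | 6.2% |
| 24:36 | 10.7% | 5.0% | 7.7% |
| 36:24 | 2.1% | 5.0% | not run |
| 12:12 | 5.9% | 5.1% | not run |

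The uneven splits are illustrations, not figures from the plan.

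**4. Mann-Whitney.** Read as a test of equal means (SD 2/0.5, normal data, 60,000 runs), it rejects 7.3% of the time at 36:36 and 9.7% at 24:36.

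**5. Skewed data.** Lognormal values shifted to equal means, SD 2/0.5, 200,000 runs:

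| Obese:lean | Student | Welch |
|---|---|---|
| 36:36 | 6.5% | 6.2% |
| 30:36 | 8.7% | 6.4% |
| 24:36 | 12.0% | 6.7% |
| 12:12 | 8.3% | 7.6% |

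On the log scale, lognormal data with the planned means and SDs have log SDs √ln(1 + (2/3.5)²) = 0.53 and √ln(1 + (0.5/1.5)²) = 0.32, which are still unequal. With equal log means, Student and Welch give 6.1% and 5.0% at 30:36, and 7.5% and 5.0% at 24:36.

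**6. Power at the planned difference** (normal data):

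| Obese:lean | Student | Welch |
|---|---|---|
| 36:36 | above 99.9% | above 99.9% |
| 24:36 | 99.9% | 99.6% |
| 13:13 | 91.5% | 90.0% |
| 12:12 | 89.0% | 87.1% |

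**The case against.** The plan contains no error at its own design. Student's t is close to nominal at 36:36, the stated powers are essentially right, and the fallback is expressed as equal groups, where the error is 5.9%.

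Uneven loss is not documented. The plan foresees only a few refusals, and the exclusion criteria (Section I, item 8) already remove people who fail MRI safety screening or have "Claustrophobia that will prevent participation in the MRI". The transaminase check before Visit 2 calls for evaluation, not removal. Two or three losses, all in the obese group, give 5.9% to 6.3%; the 10.7% needs a third of obese scans lost and no lean ones. A 4:1 SD ratio at equal means is also a harsh null, since the planned SD rises with the mean. Under the milder pair, 34:36 gives 5.4%.

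Welch is not exact for skewed raw data and gains little there at equal numbers. Moving to the log scale changes the target from a difference in means to a ratio of geometric means. The Mann-Whitney figures count as errors only if that test is read as comparing means, which is not its null hypothesis.

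All of this stands, and it limits the point to minor. It does not remove it. Nothing else in the document supplies an unequal-variance test, the log option is written for the Visit 1 outcome, and the final scan numbers cannot be known when the test is chosen. In every skewed case run, Welch was closer to nominal than Student's t.

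**Conclusion.** The point holds and is minor. The named tests do not match the plan's own variance assumptions, but the consequence is small unless scans are lost unevenly. For normal data with SDs of 2 and 0.5, Student's t is within about one percentage point of nominal at equal sizes. It reaches 7.5% if six obese scans are lost and no lean ones, and goes beyond that only with heavier one-sided loss. With a narrower SD ratio the excess is smaller. The conclusion at the planned difference would be the same with either test; the benefit of Welch lies in the case where the true difference is small or absent. The stated sample size and power are not in dispute. The result rests on two-sided testing, the planned SDs, normal data except where noted, and assumed splits of lost scans.

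**What to change.** In the Visit 2 Statistical Analysis text, name Welch's unequal-variance t-test for hepatic fat fraction in place of Student's t, fixed before scan numbers are known. If Mann-Whitney is kept, say when it applies and that it is not a test of means.

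Optionally, provide that markedly skewed data will be analysed by Welch's test on the natural-log scale and reported as a ratio of geometric means, noting that this changes the quantity estimated.

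If Welch is adopted, restate the fallback in the Sample Size text as about 87% power at 12 per group, or 90% at 13, for normal data.

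The cost is one sentence and one restated number, plus about 2 points of power at the 12-per-group floor (89.0% to 87.1%). At 36 per group the loss of power is negligible.

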- i. the types of future research to be conducted using the materials, specifying if immortalization of cell lines, whole exome or genome sequencing, genome wide association studies, or animal studies are planned *Write here*
- ii. the plan for the collection of material or the conditions under which material will be received *Write here*
- iii. the types of information about the donor/individual contributors that will be entered into a database *Write here*
- iv. the methods to uphold confidentiality *Write here*

B. What are the conditions or procedures for sharing of materials and/or distributing for future research projects? *Write here*

C. Is widespread sharing of materials planned? *Write here*

D. When and under what conditions will materials be stripped of all identifiers? *Write here*

E. Can donor-subjects withdraw their materials at any time, and/or withdraw the identifiers that connect them to their materials? *Write here*

- i. How will requests to withdraw materials be handled (e.g., material no longer identified: that is, anonymized) or material destroyed? *Write here*

F. Describe the provisions for protection of participant privacy *Write here*

G. Describe the methods for the security of storage and sharing of materials *Write here*

6. **Subject Population:** Provide a detailed description of the types of human subjects who will be recruited into this study.

This study aims to enroll 36 obese/overweight adolescents and 36 lean adolescents with T1D. A comparison control group of 36 lean young adults with T1D matched for gender and HbA1c will also be enrolled, since they will be unaffected by the adverse metabolic effects of puberty or obesity.

7. **Subject classification:** Check off all classifications of subjects that will be specifically recruited for enrollment in the research project. Will subjects who may require additional safeguards or other considerations be enrolled in the study? If so, identify the population of subjects requiring special safeguards and provide a justification for their involvement.

 Children	 Healthy	 Fetal material, placenta, or dead fetus
 Non-English Speaking	 Prisoners	 Economically disadvantaged persons
 Decisionally Impaired	 Employees	 Pregnant women and/or fetuses

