- Body composition (fat %, fat mass, lean mass)
- Abdominal fat distribution (visceral and subcutaneous)

Adjusted associations of these assessments with measures of insulin sensitivity indices obtained in Aim 1 will be explored for both groups, as described in the analysis plan for Aim 1.

SECTION II: RESEARCH INVOLVING DRUGS, BIOLOGICS, RADIOTRACERS, PLACEBOS AND DEVICES

A. RADIOTRACERS

 N/A

B. DRUGS/BIOLOGICS

 N/A

1. If an **exemption from IND filing requirements** is sought for a clinical investigation of a drug product that is lawfully marketed in the United States, review the following categories and complete the category that applies (*and delete the inapplicable categories*):

Not Applicable

2. **Background Information:** Provide a description of previous human use, known risks, and data addressing dosage(s), interval(s), route(s) of administration, and any other factors that might influence risks. If this is the first time this drug is being administered to humans, include relevant data on animal models.

All substances are non radioactive and have been extensively used in pediatric research in the last 15 years by our team with no side effects or adverse effects. Recent studies involving minors using glucose and glycerol isotopes performed by members of our research team are listed below. In addition, we have included dosing from a publication from this summer, which clarifies the rationale for dosing in youth with type 1 diabetes in HIC# [REDACTED] and the study proposed herein.

[REDACTED]	[REDACTED]	[REDACTED]	[REDACTED]	[REDACTED]	[REDACTED]
[REDACTED]	[REDACTED]	[REDACTED]	[REDACTED]	[REDACTED]	[REDACTED]
[REDACTED]	[REDACTED]	[REDACTED]	[REDACTED]	[REDACTED]	[REDACTED]
[REDACTED]	[REDACTED]	[REDACTED]	[REDACTED]	[REDACTED]	[REDACTED]
[REDACTED]	[REDACTED]	[REDACTED]	[REDACTED]	[REDACTED]	[REDACTED]
[REDACTED]					
[REDACTED]	[REDACTED]	[REDACTED]	[REDACTED]	[REDACTED]	[REDACTED]

3. **Source:** Identify the source of the drug or biologic to be used. There is no study drug (treatment) for this protocol. However, isotopes will be obtained from Cambridge Isotopes, Cambridge, MA, which is routinely audited internally by its QA department and externally by customers, notified bodies, and regulatory agencies (e.g. FDA). Isotopes will be stored in the Investigational Pharmacy and will be prepared before the subjects undergo tests.

a) Is the drug provided free of charge to subjects? YES NO
If yes, by whom? Study funding

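### The Visit 2 plan names only unadjusted tests for the lean-obese difference in liver fat and does not clearly extend the Visit 1 regression to it, although no matching between the adolescent groups is stated

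*Combined protocol and SAP*

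**What the plan says.** All of this is in the combined protocol and SAP, Section I.

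- **Visit 2 group comparison** (item 13, Visit 2 Statistical Analysis): "Continuous variables will be compared between the lean and obese adolescents using either the" Student t-test or the Mann-Whitney U test. No covariates are named.
- **Other Visit 2 liver-fat analysis** (same place): "Associations of the following assessments with hepatic fat fraction will be explored through Spearman Correlation". The listed assessments are body composition and abdominal fat distribution. This is also without covariates.
- **The one adjusted Visit 2 analysis** (end of the Visit 2 text): "Adjusted associations of these assessments with measures of insulin sensitivity indices obtained in Aim 1 will be explored for both groups". The sentence then refers back to the Aim 1 analysis plan.
- **Visit 1** (item 13, Visit 1 Statistical Analysis): the two-sample tests are labelled unadjusted and are followed by a regression: "The impact of group, gender, sex hormones, pubertal stage, and growth factors on the outcome measures will also be explored using multivariable linear regression modeling".
- **Matching** (item 6, Subject Population): "A comparison control group of 36 lean young adults with T1D matched for gender and HbA1c". Item 4 (Research Plan) states that the young adults do not attend Visit 2. No matching, stratification or quota is stated between the two adolescent groups.
- **Shared limits** (item 8): both adolescent groups must be aged 12-16, Tanner stage 2-5, with HbA1c of 9% or less and diabetes for at least 12 months.

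**The concern.** Lean and obese adolescents are not randomised. If the groups differ in gender mix or pubertal stage, and either is related to liver fat, the two-sample difference carries part of that relation along with the effect of adiposity. The plan recognises this for the same adolescents at Visit 1, where it follows the unadjusted tests with a regression on gender and pubertal stage. For Visit 2 it gives no equivalent and no reason for leaving it out.

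The lean-obese difference in PDFF is the contrast on which Visit 2 is sized, and the Innovation text presents it as one of the study's novel elements. High power gives no protection here: a larger sample makes the estimate more precise but does not remove systematic imbalance.

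**Working it through.** **1. The plan's own figure.** Inputs from the Visit 2 sample-size text: means 3.5 (SD 2) and 1.5 (SD 0.5), alpha 0.05 (two-sided assumed), 36 per group, with a fallback of 12.

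- Difference = 3.5 - 1.5 = 2.0. Pooled SD = sqrt((2² + 0.5²)/2) = 1.458.
- 36 per group: 2.0/(1.458 × sqrt(2/36)) = 5.82. Power is 99.99%, so the stated figure of more than 99% reproduces.
- 12 per group: 2.0/(1.458 × sqrt(2/12)) = 3.36. Power is 91.9% (normal), 89.4% (noncentral t) or 87.1% (Welch). The stated 90% reproduces within 2 points by the first two methods.

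The Visit 2 power statement is not in dispute.

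**2. How large an imbalance chance alone can give.** Assume both groups come from populations with a 50:50 gender split.

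- 36 per group: SD of the difference in share = sqrt(2 × 0.25/36) = 11.8 percentage points. The 95% range is ±23 points. A gap of 20 points or more (20/11.8 = 1.70 SD) has probability about 9%; 30 or more (2.55 SD) about 1%.
- 12 per group: SD = sqrt(2 × 0.25/12) = 20.4 points.

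Systematic differences in who is recruited would add to this. The documents neither show nor exclude them.

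**3. How large a gender effect the plan's figures allow.** The documents give no effect of gender on PDFF. With a 50:50 split, a constant effect b contributes variance b²/4 within each group. The lean variance is 0.5² = 0.25, so b²/4 ≤ 0.25 and b ≤ 1.0 point. At that ceiling gender would explain all the variation among lean adolescents. A working range of 0.3-0.5 points corresponds to 0.0225/0.25 = 9% and 0.0625/0.25 = 25% of the lean variance.

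**4. Bias = imbalance × effect.**

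| Effect (points) | Imbalance 20 points | Imbalance 30 points |
|---|---|---|
| 0.3 | 0.06 (3% of 2.0) | 0.09 (4.5%) |
| 0.5 | 0.10 (5%) | 0.15 (7.5%) |
| 1.0 (ceiling) | 0.20 (10%) | 0.30 (15%) |

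If there were no true group difference, a bias of 0.05 points would raise the rejection rate at 36 per group from 5% to 5.2%, and a bias of 0.15 would raise it to 7.1% (noncentral t, SD 1.458).

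**5. Power after adjustment.** Gender takes 1 degree of freedom and Tanner stage 3. Let R² be the share of the group indicator explained by these covariates, assumed 0 to 0.3. The variance of the group effect is multiplied by 1/(1 - R²), and no credit is given for residual variance that the covariates explain.

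| Per group | R² = 0 | R² = 0.1 | R² = 0.2 | R² = 0.3 |
|---|---|---|---|---|
| 36 | 99.99% | 99.97% | 99.9% | 99.8% |
| 12 | 88.8% | 85.4% | 81.1% | 75.8% |

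**The case against.** The strongest reply is that adjustment is already intended. The Visit 1 regression is described for outcome measures in general, and the Visit 2 text ends by pointing to the Aim 1 plan. That reading is possible but not secure. The pointer is attached to associations with the insulin indices, not to the group difference in PDFF. The Visit 1 model also does not transfer as written: it has three groups and two pairwise comparisons at 0.025, while Visit 2 has two groups and is sized at 0.05. If the wider meaning was intended, a sentence would settle it.

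Three further points stand and limit the concern.

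- A reader might infer that Aim 2 as a whole is unadjusted. It is not. The Statement of Purpose words that aim as the role of fatty liver disease in the insulin resistance of obesity, and the Visit 2 analysis that brings in the insulin indices is adjusted. The gap is in the group contrast.
- A reader might infer that nothing makes the adolescent groups comparable. The shared eligibility limits bound the imbalance, as do the exclusions for other liver disease and for drugs affecting insulin sensitivity, although Tanner 2-5 is wide. The text also does not say to whom the young adults are matched. If they were matched to both adolescent groups, gender mix would have to be similar, but the documents do not say so.
- An unadjusted test is a valid description of how two groups differ, and the planned descriptive statistics would show an imbalance. They would not show how much of the PDFF difference it accounts for.

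**Conclusion.** The point holds for the lean-obese comparison of PDFF and abdominal fat: only two-sample tests are named, and no matching between these groups is stated. Under a constant gender effect of 0.3-0.5 points and an imbalance of 20-30 percentage points, the planned 2.0-point difference would move by about 0.06-0.15 points (3% to about 8%). The direction is unknown.

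A reader might infer that confounding could produce or overturn the projected result. The documents do not support that. Even the ceiling case in the table leaves 1.7 of the 2.0 points, and it requires gender to explain all the lean variance. The bias would matter more if the true difference were smaller than planned.

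Two limits apply. The ceiling holds for a constant effect and a 50:50 split; a larger effect confined to the obese group (SD 2) is not excluded. Pubertal stage is not quantified, and its bias could add to that from gender or offset it.

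**What to change.** Add to the Visit 2 Statistical Analysis a linear regression of PDFF on group, gender and pubertal stage, using the natural log if needed as Visit 1 already allows. Use the same model for visceral and subcutaneous fat. Report the adjusted group difference with its confidence interval beside the two-sample test, and label the latter as unadjusted. Keeping both results visible also serves readers who regard pubertal stage as part of the pathway.

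The cost is a few lines of SAP wording and one extra model per outcome. No new data are needed, because both covariates are already in the Visit 1 model. The power loss is negligible at 36 per group. At the 12-per-group fallback, power would be about 76-89% if the covariates explain no residual variance, so the fallback statement should say that its 90% refers to the unadjusted test.
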